9.7.1.6.2. Safety Labs (Chemistry and Hematology)

Descriptive summaries of the observed test results at Visits 1 and 6 as well as the change from baseline at Visit 6 will be presented for serum chemistry and hematology labs. The frequency and percentage of subjects with observed values of Low, Normal, High as well as the categorical shift from baseline at Visit 6 will be tabulated. The percentages are calculated based on the number of subjects at each visit in each treatment group of the Safety Analysis Set.

It is expected that all samples will be analyzed by a central laboratory. If a local laboratory is used (such as for an unscheduled visit), the results will be included in the listings of laboratory data, but will not be included in descriptive summaries.

The results of pregnancy tests for women of childbearing potential will be presented in a listing.

9.7.1.6.3. Best Corrected Visual Acuity (BCVA)

Descriptive summaries of the observed values of LogMAR at each scheduled visit as well as the change from baseline at each post-baseline visit will be presented for both eyes. A categorical analysis of subjects who lose 0.3 lines ETDRS in either eye at each visit will be conducted.

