9.4.3.3 Other Safety Evaluations

Summary statistics for observed and CFB for BCVA, IOP, and drop comfort assessment will be presented. Abnormalities in slit lamp biomicroscopy and dilated ophthalmoscopy will be summarized by frequency and percentage.

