12.9 Appendix 9: Best Corrected Visual Acuity (BCVA)

Visual acuity (VA) testing should precede any examination requiring contact with the eye or instillation of study dyes, as is detailed in the order of assessments for each visit in [Section 7.1](#). LogMAR visual acuity must be assessed using an ETDRS or modified ETDRS chart. VA testing should be performed with best correction using subject's own corrective lenses (spectacles only) or pinhole refraction.

An ETDRS or modified ETDRS chart may be used. If a Lighthouse chart is used (24.5" by 25"; either reflectance or retro-illuminated), the subject must view the chart from a distance of exactly 4 meters (13.1 feet). If smaller reproductions (18" by 18", e.g., Prevent Blindness) are used, the subject viewing distance should be exactly 10 feet. Reflectance wall charts should be frontally illuminated (60-watt bulb or a well-lit room).

The subject should be positioned according to the elevation of the chart (either seated or standing) so that the chart is at a comfortable viewing angle. The right eye should be tested first. The subject should attempt to read each letter, line-by-line, left to right, beginning with line 1 at the top of the chart. The subject should be told that the chart has letters only, no numbers. If the subject reads a number, he or she should be reminded that the chart contains no numbers, and the examiner should then request a letter instead of the number. The subject should be asked to read slowly, about 1 letter per second, to achieve the best identification of each letter. He/she is not to proceed to the next letter until he/she has given a definite response. If the subject changes a response before he has read aloud the next letter, then the change must be accepted.

Maximum effort should be made to identify each letter on the chart; the subject should be encouraged to guess. When it becomes evident that no further meaningful readings can be made, the examiner should stop the test. The number of letters missed or read incorrectly should be noted.

In order to provide standardized and well-controlled assessments of visual acuity during the study, the same lighting conditions must be used consistently throughout the study

Calculations: LogMAR VA = Baseline value + (n X 0.02)

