9.5.1.4.3. Best Corrected Visual Acuity (BCVA)

The BCVA is measured on both eyes in LogMAR at every in-clinic visit. LogMAR is calculated as Baseline value + (n × 0.02); where the baseline value is the LogMAR number of the last line read (at least one letter read correctly in this line), "n" is the total number of letters missed up to and including the last line read, and "0.02" is the value for each letter.

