9.7.1. Statistical and Analytical Plans

General Conventions

Summary statistics for the data collected during this study will be presented to give a general description of the subjects studied. Data from all sites will be combined in the computation of these descriptive summaries. Categorical variables will be summarized by the frequency and percentage of subjects in each category. Continuous variables will be summarized using N, mean, standard deviation (SD), median, minimum, and maximum values.

Number of subjects, minimums, and maximums will be calculated to the same number of decimal places as the source data. Means, medians, standard deviations, and quartiles will be calculated to one more decimal place than the source data. Percentages will be calculated to the nearest one decimal place. Zero count cells will be displayed as "0" with percentage of (0%). Unless otherwise noted, summaries will be performed by the treatment group and presented in the order of: SY-201 2.0% or 1.0% or 0.5% (efficacy analyses only), SY-201, 2.0%; SY-201, 1.0%; SY-201, 0.5%; Vehicle.

Statistical tests will be presented as two-sided p-values rounded to four decimal places; p-values less than 0.0001 will be presented as '<0.0001' and p-values = 1 will be presented as '>0.9999' in all tables. Unless otherwise indicated, statistical testing will be carried out at the $\alpha = 0.05$ significance level.

Baseline values will be defined as the last measurement prior to dosing of double-masked study medication. Ocular measurements will use the most recent measurement for each eye.

Numeric laboratory data may be recorded at limits of detection (with a '<' or '>' sign, i.e. < 0.1 or > 0.1). To summarize the data, the original value will be converted to one unit less or more at the level of measured precision (e.g. 0.4 in the case of < 0.5 and to 0.6 in the case of > 0.5). The actual values will be presented in the data listings.

MMP-9 data may be recorded at limits of detection of < 5 ng/mL or > 1000 ng/mL. To summarize the data, the original value will be converted to either 4 ng/mL or 1010 ng/mL, respectively. The actual values will be presented in the data listings.

All data collected in this study will be presented in individual subject data listings for all subjects.

Computations for all results will be performed using SAS (Version 9.4, SAS/STAT 15.2) computer software package (SAS Institute, Inc, 2013, 2020), unless otherwise specified.

Strata and Covariates

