9.7.1.6. Analysis of Safety

Safety will be evaluated by:

1. Adverse event (AE) monitoring
2. Safety labs (chemistry and hematology)
3. Best Corrected Visual Acuity (BCVA)
4. Slit lamp biomicroscopy and external eye exam
5. Intraocular pressure (IOP)
6. Dilated ophthalmoscopy
7. Drop comfort assessment

The Safety Analysis Set will be used for all safety analyses. All data will be summarized as observed, and no data imputation will be performed. No statistical treatment group comparisons

will be performed, unless otherwise specified. Analyses will be presented by study eye and non-study eye, if applicable.

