9.7.1.6.5. Intraocular Pressure (IOP)

Descriptive summaries of the observed values at each scheduled visit as well as the change from baseline at each post-baseline visit will be presented for both eyes. A categorical analysis of subjects who gain 10 mmHg or more in IOP at each visit will be conducted.

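### The SAP's only categorical vision-loss rule is set at 0.3 ETDRS lines, a threshold that does not fit LogMAR letter scoring and is ten times smaller than 0.3 LogMAR

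*SAP*

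**What the plan says.** The SAP sets one categorical rule for loss of vision, in 9.7.1.6.3: "A categorical analysis of subjects who lose 0.3 lines ETDRS in either eye at each visit will be conducted". The sentence before it in the same section summarises observed values and change from baseline in LogMAR.

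The measurement scale is LogMAR throughout. SAP 9.5.1.4.3 says "The BCVA is measured on both eyes in LogMAR at every in-clinic visit", and both documents score 0.02 per letter missed: "LogMAR is calculated as Baseline value + (n × 0.02") in the SAP and "Calculations: LogMAR VA = Baseline value + (n X 0.02") in Protocol Appendix 9. Neither says how many letters make a line or converts lines to LogMAR.

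The protocol has no categorical vision-loss threshold to fall back on. Its section 9.4.3.3 says only: "Summary statistics for observed and CFB for BCVA, IOP, and drop comfort assessment will be presented". The LogMAR limits in the entry criteria govern eligibility, not loss during the study.

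The parallel rule for intraocular pressure, SAP 9.7.1.6.5, is complete: "A categorical analysis of subjects who gain 10 mmHg or more in IOP at each visit will be conducted".

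**The concern.** The threshold is given in a unit (lines) on which the trial does not record acuity, and at a value (0.3) that is a fraction of a line and not a whole number of letters. The figure 0.3 is a natural LogMAR value, so a unit slip is plausible, but the text does not say so. The rule also omits *or more*, so even its direction is left to convention.

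Ocular safety is part of the primary objective and BCVA is a named safety endpoint. This is the only analysis in either document that counts subjects with vision loss. If the cut is taken as a fraction of a line, the table fills with test-retest noise and a real signal would be hard to see in it. If the cut is chosen after unmasking, the safety count depends on a decision made with the data in view.

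**Working it through.** **Inputs from the documents**
- Scoring step: 0.02 LogMAR per letter (SAP 9.5.1.4.3; Protocol Appendix 9).
- Threshold as written: 0.3 lines, either eye, each visit (SAP 9.7.1.6.3).
- Planned arm size: 50.

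**Assumptions, not in the documents**
- Five letters per line, with four and six also shown.
- For the illustration of size: no true change; normally distributed change between visits with SD 0.04 to 0.10 LogMAR; correlation between a subject's two eyes of 0, 0.5 or 0.8.

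The threshold is a stated rule rather than a derived quantity, so there is no plan figure to reproduce first.

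**Step 1: convert the units.**

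Letters = 0.3 × letters per line; LogMAR = letters × 0.02.

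| Letters per line | 0.3 lines in letters | 0.3 lines in LogMAR |
|---|---|---|
| 4 | 1.2 | 0.024 |
| 5 | 1.5 | 0.030 |
| 6 | 1.8 | 0.036 |

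None of these is a whole letter, so none is an observable change. In each case the smallest observable loss that reaches the cut is two letters (0.04 LogMAR).

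From the documents' own step alone, 0.3 LogMAR = 0.3 / 0.02 = 15 letters. At five letters per line, the ratio of the two thresholds is 0.30 / 0.03 = 10.

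**Step 2: list the readings.**
1. Exactly 0.3 lines, as literally written: no eye can show a 1.5-letter loss, so 0 subjects are flagged.
2. 0.3 lines or more: every loss of two or more letters is flagged.
3. 0.3 LogMAR or more: every loss of 15 or more letters is flagged.

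**Step 3: how many subjects would each flag by chance?**

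Because scores move in whole letters, the normal tail is taken half a letter below the smallest flagged loss. For reading 2 that is 1.5 letters, or 0.03 LogMAR; for reading 3 it is 14.5 letters, or 0.29 LogMAR.

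Per eye, p = 1 − Φ(cut / SD). At SD 0.04, for example, p = 1 − Φ(0.03 / 0.04) = 1 − Φ(0.75) = 22.7%.

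For either eye with independent eyes, the proportion is 1 − (1 − p)². At SD 0.04 this is 1 − 0.773² = 40.2%. For correlated eyes it is 1 minus the bivariate normal probability that both eyes stay below the cut.

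Reading 2:

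| SD (LogMAR) | Per eye | Either eye, corr. 0 | Either eye, corr. 0.5 | Either eye, corr. 0.8 |
|---|---|---|---|---|
| 0.04 | 22.7% | 40.2% | 34.9% | 30.3% |
| 0.06 | 30.9% | 52.2% | 45.4% | 39.9% |
| 0.08 | 35.4% | 58.2% | 50.8% | 44.9% |
| 0.10 | 38.2% | 61.8% | 54.1% | 48.0% |

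Per arm of 50, the lowest either-eye figure gives 50 × 0.303 = 15.2 subjects and the highest gives 50 × 0.618 = 30.9.

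Reading 3, at the largest SD (0.10): 1 − Φ(2.9) = 0.19% per eye, and 1 − (1 − 0.0019)² ≈ 0.37% in either eye with independent eyes. That is 50 × 0.0037 ≈ 0.2 subjects per arm. Smaller SDs give less.

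**The case against.** The best counter-argument is that the intent can be inferred. The neighbouring sentence is in LogMAR, and a misplaced decimal for 3 lines would, at five letters per line, give the same 15 letters as a wrong unit word for 0.3 LogMAR. The two natural explanations of the slip therefore agree. The exact-value reading is also not how a loss threshold is normally taken, and reading 2 produces so uninformative a table that a programmer would probably raise a query.

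This has force. It makes 0.3 LogMAR the likely intent and reading 1 improbable. It does not put that threshold in the plan: applied as written with *or more* supplied, the rule gives the two-letter cut, and any other value is the programmer's inference about a safety threshold.

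A second objection is that little depends on the table. SAP 9.7.1 says "Continuous variables will be summarized using N, mean, standard deviation (SD), median, minimum, and maximum values", so the largest LogMAR losses would appear as extremes of the change summaries. All data are listed, and vision loss reported as an adverse event would appear in the ocular event tables by eye. For safety, SAP 9.7.1.6 plans "No statistical treatment group comparisons" unless otherwise specified, and the categorical table goes beyond what the protocol requires. All of this stands, and it limits the consequence. It does not make the threshold right.

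The percentages do rest on an SD and correlations from outside the documents and are illustrative only. The unit mismatch needs no outside assumption; the tenfold gap needs only five letters per line.

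**Conclusion.** The concern holds: the rule is wrong as written. A cut of 0.3 lines is 0.03 LogMAR at five letters per line, is unobservable at four, five or six letters per line, and is a tenth of 0.3 LogMAR. Nothing else in either document settles which value is meant.

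Under the stated noise assumptions, the same data could give a table with essentially no vision loss, or one that flags somewhere between three and six subjects in ten at each visit. The lower end of that contrast does not depend on the improbable exact-value reading, because the 15-letter cut also gives close to zero.

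The damage is limited to one descriptive safety table. This should be corrected, but it does not threaten the trial's main conclusions.

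**What to change.** Before unmasking, have the sponsor confirm the intended threshold. Then restate SAP 9.7.1.6.3 in LogMAR with the letter equivalent, *or more*, and an explicit reference to baseline (already defined in SAP 9.7.1), in the form of the intraocular pressure rule.

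If 0.3 LogMAR is confirmed, suitable wording would be: *subjects with an increase from baseline of 0.3 LogMAR or more (15 or more letters) in either eye at each visit*. If another value was intended, the same form applies with that value.

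The cost is a one-line correction to the SAP. It needs no new data and changes no inferential analysis.

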9.7.1.6.4. Slit Lamp Biomicroscopy and External Eye Exam

The frequency and percentage of subjects with observed values of each categorical response or grade as well as the categorical shift from baseline at each post-baseline visit will be tabulated at each scheduled visit for both eyes. The percentages are calculated based on the number of subjects at each visit in each treatment group of the Safety Analysis Set.

9.7.1.6.5. Intraocular Pressure (IOP)

Descriptive summaries of the observed values at each scheduled visit as well as the change from baseline at each post-baseline visit will be presented for both eyes. A categorical analysis of subjects who gain 10 mmHg or more in IOP at each visit will be conducted.

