7.1.7 Unscheduled Visits

At times outside of normally scheduled visits, assessments will be conducted at the discretion of the Investigator.

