7.1.8 Early Termination

In the event that a subject exits or is terminated from the study prior to the End of Study visit (Visit 6), every attempt will be made to ensure that all Visit 6 assessments are performed prior to the subject being discharged.

8. Study Assessments

The Schedule of Procedures and Assessments ([Appendix 1](#)) provides a list of study assessments and evaluations to be performed and the timing of each.

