9.5.1.4. Safety Assessments

The safety of SY-201 Ophthalmic Solution will be evaluated using the following assessments, conducted at each in-clinic visit unless otherwise noted.

1. Adverse event (AE) monitoring
2. Safety labs (chemistry and hematology) – Visits 1 and 6
3. Best Corrected Visual Acuity (BCVA)
4. Slit lamp biomicroscopy and external eye exam
5. Intraocular pressure (IOP)
6. Dilated ophthalmoscopy – Visits 1 and 6
7. Drop comfort assessment – Visits 2 and 6

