For analysis of efficacy endpoints, longitudinal models will model the change from baseline of each endpoint as the dependent variable with the baseline measurement of the corresponding endpoint as a covariate and treatment group as the main effect. A random effect for site will be added to account for site-to-site variability.

Subgroups

Subgroup analyses will include testing of the mean CFB in tCFS,

Subgroup analyses by sex and age group (<65 years, ≥65 years) may also be performed.

Multiplicity

To control for type I error, comparisons will be made within each active dose level of SY-201 Ophthalmic Solution compared to Vehicle. In other words, the primary endpoints will be compared sequentially between SY-201 Ophthalmic Solution 2.0% and Vehicle, first testing tCFS and, if statistically significant, . Should both endpoints achieve statistical significance for the 2.0% dose, testing will proceed to Y-201 Ophthalmic Solution 1.0% versus Vehicle, first testing tCFS and, if statistically significant, . Should both endpoints achieve statistical significance for the 1.0% dose, testing will proceed to SY-201 Ophthalmic Solution 0.5% and Vehicle, first testing tCFS and, if statistically significant, . In other words, the first non-significant result in this testing hierarchy of six hypotheses will imply that subsequent tests are non-significant.

Missing Data and Outliers

Every attempt will be made to capture all study data. All analyses will utilize observed data only. Analysis of continuous efficacy endpoints using MMRM assumes missing at random (MAR). Sensitivity analyses of the primary endpoints will be performed utilizing control-based pattern imputation, last observation carried forward (LOCF), and baseline observation carried forward (BOCF).

Visit Windows

The nominal visits listed in the eCRF will be used in the summaries. In general, unscheduled visits will not be summarized in tables unless otherwise noted.

Missing Dates

Missing dates that occur for prior or concomitant medications or adverse events will be queried for a date. If no date is obtained, the following imputation rules will apply:

- For start dates, if the given year (or year-month) is the same as study drug administration, the start date will be imputed as study drug administration date; otherwise, missing month-day (or day) will be imputed as '01-01' (or '01').

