9.7.1.5. Analysis of Efficacy

Summary descriptive statistics will be presented for all study visits at which efficacy data are collected. Efficacy analyses will be presented by the study eye and non-study eyes.

For subjects who discontinue treatment prior to Visit 6, data collected using Early Termination eCRFs will not be summarized separately unless the termination occurred on a scheduled visit (within the visit windows of a particular visit).

All longitudinal models will be fit using the MIXED procedure in SAS. Categorical analyses will be conducted using the FREQ procedure.

All efficacy analyses will be conducted using the FAS Analysis Sets.

To control for type I error, comparisons will be made within each active dose level of SY-201 Ophthalmic Solution compared to Vehicle. In other words, the primary endpoints will be compared sequentially between SY-201 Ophthalmic Solution [REDACTED] and Vehicle, first testing tCFS and, if statistically significant, [REDACTED]. Should both endpoints achieve statistical significance

for the [REDACTED] testing will proceed to SY-201 Ophthalmic Solution [REDACTED] versus Vehicle, first testing tCFS and, if statistically significant, [REDACTED]. Should both endpoints achieve statistical significance for the [REDACTED] testing will proceed to SY-201 Ophthalmic Solution [REDACTED] and Vehicle, first testing tCFS and, if statistically significant, [REDACTED]. In other words, the first non-significant result in this testing hierarchy of six hypotheses will imply that subsequent tests are non-significant.

Testing of all active doses combined compared to vehicle will also be performed.

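### The IOP-rise and vision-loss criteria are tabulated only visit by visit and by default without unscheduled visits, so the tables can understate how many subjects per arm ever meet them

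*SAP*

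**What the plan says.** SAP 9.7.1.6.5 plans, for intraocular pressure (IOP): "A categorical analysis of subjects who gain 10 mmHg or more in IOP at each visit will be conducted". SAP 9.7.1.6.3 plans, for best corrected visual acuity (BCVA): "A categorical analysis of subjects who lose 0.3 lines ETDRS in either eye at each visit will be conducted". Neither section adds a row for any post-baseline visit or a worst-value summary, and no other part of SAP 9.7.1.6 supplies one.

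Two general rules in SAP 9.7.1, under Visit Windows, decide what enters a table: "The nominal visits listed in the eCRF will be used in the summaries", and "In general, unscheduled visits will not be summarized in tables unless otherwise noted". Neither the IOP nor the BCVA section notes an exception.

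Examinations between visits can occur. Protocol 7.1.7 says: "At times outside of normally scheduled visits, assessments will be conducted at the discretion of the Investigator".

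SAP 9.5.1.4 has the safety assessments "conducted at each in-clinic visit unless otherwise noted", and no exception is noted for IOP or BCVA. Both are therefore measured at four scheduled post-baseline visits (Visits 3 to 6).

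**The concern.** Ocular safety is part of the primary objective (Protocol 2.1), IOP and BCVA are named safety endpoints (Protocol 2.2.3), and the trial compares three concentrations with vehicle. A reader judging ocular safety by dose will ask how many subjects in each arm ever had a marked pressure rise or vision loss. The planned tables do not answer that. They give one percentage per visit and do not show whether the same or different subjects are behind each one. A subject whose only qualifying value was recorded at an unscheduled visit would, under the default rule, appear in no column of the IOP or BCVA table.

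The SAP already uses the cumulative approach for adverse events. SAP 9.7.1.6.1 counts each subject once per term over the whole treatment-emergent period. The two threshold criteria have no equivalent.

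The size and unit of the vision threshold are a separate matter and play no part here.

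**Working it through.** The plan states no figure on this point, so there is none to reproduce. The check is a reading of the rules followed by an illustration of size.

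**Inputs**
- Subjects per arm: 50 (SAP 9.7.2).
- Scheduled post-baseline visits with IOP and BCVA: 4 (Visits 3 to 6, SAP Appendix I).
- Probability *p* of meeting a criterion at a given visit: not in the documents. Assumed 1% to 5%.
- Correlation between visits within a subject: not in the documents. Taken as 0 (independent) to 0.8 on a latent normal scale.

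**Step 1. What per-visit columns can tell.** For scheduled visits, the number who ever meet a criterion lies between the largest per-visit count and the sum of the per-visit counts. Suppose each of the four columns shows 1 of 50, which is 2%. One subject meeting the criterion four times gives 1/50 = 2% ever. Four different subjects give 4/50 = 8% ever. The columns are the same in both cases, so the any-time figure cannot be recovered from them. The 8% is the no-overlap maximum for these columns, not an expected value.

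**Step 2. Unscheduled values.** One further subject, with a 12 mmHg rise seen only at an unscheduled visit, adds 0 to every column and 1/50 = 2% to an any-time count. Such values can only raise the any-time count.

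**Step 3. Expected size, scheduled visits only.** With independent visits, the expected number ever meeting the criterion is 50 × [1 − (1 − *p*)^4]. At *p* = 2% this is 50 × (1 − 0.98^4) = 50 × 0.0776 = 3.9. The values for correlation 0.8 come from a simulation of 40,000 arms of 50 with a shared subject effect and full attendance.

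| Assumed *p* per visit | Expected at one given visit | Ever, correlation 0.8 | Ever, independent | Arms in which the ever-count exceeds the largest single-visit count |
|---|---|---|---|---|
| 1% | 0.5 | 1.2 | 2.0 | 20% to 51% |
| 2% | 1.0 | 2.3 | 3.9 | 45% to 85% |
| 5% | 2.5 | 5.3 | 9.3 | 83% to 99.7% |

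The expected any-time count is about 2.1 to 3.9 times the expected count at one visit. A reader who looks at the worst column gets closer, but not all the way. At *p* = 2% the largest single-visit count averages 1.7 (correlation 0.8) to 2.1 (independent), against 2.3 to 3.9 ever.

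**The case against.** **The per-visit tables are correct for what they report.** This is true. The largest column equals the any-time count if everyone affected qualifies at one common visit and no unscheduled value adds anyone. The claim is therefore that the tables can understate, not that they must.

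**The exclusion of unscheduled visits is soft.** The rule in SAP 9.7.1 is a general one that allows exceptions. The categorical sentences also omit the word scheduled, which the descriptive sentences beside them include. That leaves some room, but no exception is noted and the default governs.

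**Nothing is lost.** All data are listed (SAP 9.7.1). An affected subject also enters cumulative tables by arm if an adverse event is reported (SAP 9.7.1.6.1). This mitigates the gap without closing it. Listings give no incidence by arm, and the documents do not make a 10 mmHg rise an adverse event in itself, so that route depends on the Investigator.

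**It is a reporting preference.** Protocol 9.4.3.3 promises only summary statistics for IOP and BCVA, and SAP 9.7.1.6 plans no treatment comparisons for safety unless specified. Both are so. But once the SAP adds a threshold analysis, the number who cross the threshold is its natural result.

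**A stronger reading.** A reader might infer that early leavers' exit examinations are also shut out, so that their laboratory and dilated ophthalmoscopy results have no Visit 6 column to enter. The source would be SAP 9.7.1.5, where "data collected using Early Termination eCRFs will not be summarized separately unless the termination occurred on a scheduled visit". The documents do not support this. The sentence belongs to the efficacy section and can mean only that early termination gets no column of its own. Both documents define Visit 6 as the end-of-study or early termination visit, and Protocol 7.1.8 says that "every attempt will be made to ensure that all Visit 6 assessments are performed prior to the subject being discharged". Exit results may well be tabulated under Visit 6. The safety section does not say how, but silence is not exclusion.

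**Conclusion.** The point holds for the two threshold criteria. As written, the plan gives no any-time count for the IOP-rise and vision-loss criteria and by default keeps unscheduled examinations out of the tables, so subjects who meet a criterion can be missing from every IOP and BCVA column. At an assumed 2% per visit, the shortfall is the gap between 1.0 expected subject at a given visit and 2.3 to 3.9 ever, per arm of 50. The sizes rest on assumed rates and correlations, full attendance and no unscheduled events, and are illustrations only. That the any-time count cannot be recovered from the columns needs no assumed rate.

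The consequence is an incomplete summary of ocular safety by dose. The data themselves are not lost, and the efficacy analyses are untouched. It is worth correcting before unmasking. The point does not extend to laboratory tests or dilated ophthalmoscopy.

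**What to change.** Add to SAP 9.7.1.6.3 and SAP 9.7.1.6.5:

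> The number and percentage of subjects in the Safety Analysis Set who meet the criterion in either eye at any post-baseline assessment, including unscheduled and early termination assessments, will also be presented. The denominator is the number of subjects with at least one post-baseline assessment of the measure.

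Naming early termination assessments makes the row independent of how exit examinations are assigned to visits. Naming either eye also settles a gap in the IOP section, whose categorical sentence specifies no eye, while the BCVA sentence does.

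The cost is two or three lines of SAP text and one row in each of two tables, from data already collected. There is one drawback. Unscheduled examinations are at the Investigator's discretion, so the any-time row depends partly on how often a subject is examined. Keep the per-visit rows beside it, since they are based on a common schedule.
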